Theorists have conjectured that the impact of AUA on suicide risk may depend on alcohol expectancies and increased suicide-related attentional bias. However, for obvious ethical reasons²⁷, no experimental tests of this hypothesis exist. Addressing these challenges, the proposed experiment is an ethical and innovative test of these hypotheses; it examines a construct theorized to occur early in the trajectory towards suicidal behavior but which has not yet been examined in relation to AUA: suicide-related attentional bias.³ This experiment complements NIAAA's strategic goals in basic science and prevention research, as it examines targetable cognitive factors that may influence suicidal ideation—a significant comorbidity among individuals with alcohol use disorders. This study challenges the current paradigm in alcohol-related suicide research in two important ways. First, it represents the first known experimental test of the AAM as it applies to suicide-related attentional bias and would guide methodology and parameters for future related studies, including those with samples higher in dysregulated mood. Further, this would be the first known study of suicide-related expectancies, another frequently hypothesized but untested correlate of alcohol-related suicide risk. If our hypotheses are supported, it would provide empirical support for a larger-scale test of the AAM as is relates to suicide risk. Future laboratory tests could test whether decreasing the salience of negative mood reduces suicide-related attentional bias. If alcohol expectancies are associated with suicide-related attentional bias, future work could test interactive effects of alcohol expectancies with mood and AUA on this bias. Downstream clinical implications include targeting expectancies and negative mood among individuals who consume alcohol. Ultimately, these findings may inform future basic and applied research examining the effects of AUA on suicidal ideation and behavior.

[figure not shown]
Approach

Consistent with theoretical and empirical work regarding the effects of AUA on suicidal thoughts and behaviors, this pilot study will test the interactive effects of Figure 2. Summary of Research Approach

AUA, negative mood, and alcohol expectancies on suicide-related attentional bias. The proposed study will employ a 2x2, between subjects design (alcohol-placebo X negative mood-positive mood, baseline levels of expectancies). See Figure 2 for a summary of our approach.

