Upon reaching a BrAC of at least .075%, a brief manipulation check will be performed. Participants will rate their level of intoxication on a scale of 0 (0=not at all) to 11 (11=more drunk than I have ever been).⁴¹ Immediately after, participants will be randomized to a 10-minute mood induction procedure. A self-referent plus musical mood induction paradigm will be employed to induce a positive or negative mood state in participants.⁴² Self-referent statements (e.g., negative or positive self-statements) and musical mood inductions are both valid, stand-alone procedures for inducing mood. The combination of both has been shown to be effective in inducing a temporary negative mood state in 75% of subjects.⁴² The combined negative mood induction paradigm was created based on a modernized version⁴³ of a seminal, self-referent mood induction⁴⁴ and a musical mood induction.⁴⁵ Participants will read 25 statements presented in a timed, PowerPoint slideshow, first to themselves and then aloud, and are instructed to "feel and experience each statement as it would apply to you personally." They will concentrate on each statement for 20 seconds and then proceed to the next one. Five statements were revised to generalize to the greater population. This is done simultaneously with the musical negative mood induction paradiam, which involves listening to a piece of music that conveys a particular mood (negative: Prokofiev's 'Russia Under the Mongolian Yoke' at half speed; positive: Delibes 'Coppelia'). These musical pieces were chosen as they are the most studied of the effective musical induction procedures.⁴⁶ Subjects will be left alone in the room during the mood induction to lessen inhibitions but will be observed by way of a window.

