Pre-Manipulation Mood and Cognition (PANAS-X; Brief Hopelessness Measure)
Manipulation Procedures and Checks
Alcohol or placebo administration; Post drinking BrAC measurement; Manipulation check
Mood induction (positive or negative); Manipulation check: PANAS-X
Outcome Measure: Modified Stroop-Suicide (primary outcome of interest), Brief Hopelessness Measure
Post-Study Procedures: Detoxification (if applicable); Post-Study Verbal Interview, Paykel Suicide Scale
(current; risk screening for post study interview), Debriefing, Payment
Follow up Wollness Check Dhone Calle (day of day following, and wook following)

Follow-up Wellness Check Phone Calls (day of, day following, and week following)

Analytic plan

H1: We will quantify the number of individuals screened and the percentage who are eligible and participate. We will run descriptive statistics to quantify 1) prevalence of successful mood induction, 2) distress ratings post-study session, and 3) number of adverse events. Using measures of effect size, t-tests, and Chi square analyses, we will examine sociodemographic differences in these feasibility factors. H2: We will use measures of effect size, t-tests, and Chi Square analyses to examine sociodemographic differences in suicide-related attentional bias scores. H3: The interactive effect of mood and AUA on suicide-related attentional bias will estimated model be using а general linear of the form $\hat{Y} = \beta_0 + \beta_1 Alcohol + \beta_2 Mood + \beta_3 Alcohol \times Mood$. **H4:** The interactive effect of alcohol expectancies and AUA on suicide-related attentional bias will be estimated using a general linear model of the form $\hat{Y} = \beta_0 + \beta_1 Alcohol + \beta_2 Expectancies + \beta_3 Alcohol \times Expectancies$. For H3 and H4, we will use linear contrasts to estimate effects. Inferences will be conducted using 68% CIs for comparisons of interest, as significance testing is not a primary study aim. See Statistical Design and Power attachment.

Potential Problems, Alternative Strategies, Benchmarks for Success, and Impact

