COVER PAGE

Official Study Title: Acute Use of Alcohol and Attentional Bias Towards Suicide: An Experimental Test of the Attention-Allocation Model

NCT number: NCT04276779

Date of the document: December 1, 2023

Statistical Design and Power

Statistical Design

Data from Qualtrics (Session 1 baseline data), excel (paper data entered from Session 1 and 2), and DirectRT software will be exported into IBM SPSS statistical software, Version 25. Standard data quality checks and cleaning procedures will be completed. Most notably, any participants voicing awareness of the study aims or not responding adequately to the mood induction will be removed from the initial analyses. Second, manipulation checks will be performed by comparing the participants in the mood conditions on self-reported mood post-manipulation. We expect that negative mood participants will have greater mean scores on the guilt and sadness subscales and lower mean scores on the joviality subscale compared to the positive mood participants.

Study variables for the entire sample will be examined using descriptive statistics such as frequencies and percentages (for categorical variables) and means, standard deviations, and ranges (for continuous variables) to ensure values are reasonable. Prior to conducting analyses related to the hypotheses of the study, individual distributions of continuous variables will be examined visually with histograms to confirm that all assumptions for the analyses are reasonably met. Methods robust to distributional assumptions will be used as appropriate.

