Specific Aim 2, Hypothesis 2: Examine sociodemographic differences in suicide-related attentional bias. Suicide-related attentional bias will be higher among women, individuals with lower income, individuals ages 21-34, and individuals with heavier alcohol use than their comparators. Although racial differences are not observed in suicide attempts, we will explore racial differences in suicide-related attentional bias.

Analysis: Using measures of effect size and *t*-tests and Chi Square analyses where appropriate, we will examine potential these sociodemographic differences in suicide-related attentional bias scores.

Specific Aim 3, Hypothesis 3: Examine the conditional effect of AUA on suicide-related attentional bias by mood states. Individuals in the alcoholic beverage-negative mood condition will exhibit the greatest suicide-related attentional bias, followed by individuals in the placebo beverage-negative mood condition, placebo beverage-positive mood condition, and alcoholic beverage-positive mood condition.

Analysis: The interactive effect of mood and alcohol (Alcohol X Mood Induction) on attentional bias towards suicide-related cues (Stroop interference score, calculated by subtracting the response latencies for neutral words from the latencies for suicide-related words) will be estimated using a general linear model of the form $\hat{Y} = \beta_0 + \beta_1 Alcohol + \beta_2 Mood + \beta_3 Alcohol \times Mood$, where \hat{Y} is the average Stroop interference score, *Alcohol* is a binary indicator (1=yes, 0=no) of assignment to alcoholic beverage intake, and *Mood* is a binary indicator of assignment to the positive vs. negative mood induction (1 vs. 0). Among the positive mood induction group, the average effect of alcohol intake on Stroop interference scores is estimated by the sum of coefficients $\beta_1 + \beta_3$, while the average effect of alcohol intake in the negative mood induction group is estimated by the coefficient β_1 . Therefore, the coefficient β_3 estimates the differential effect of alcohol intake conditional on mood induction. We will use model-predicted means to estimate mean Stroop interference scores among the negative mood-alcohol condition participants. Measures of effect size (e.g. R², partial eta², Cohen's d) will be used to aid in interpretation. Inferences will be conducted using confidence intervals for the comparisons of interest, as statistical significance testing is not the primary goal of the study.

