Specific Aim 4, Hypothesis 4: Explore the conditional effect of AUA on suicide-related attentional bias by alcohol expectancies. The relation of suicide-related alcohol expectancies with suicide-related attentional bias will be stronger among those in the AUA condition compared to those in the placebo condition.

Analysis: The interactive effect of expectancies and alcohol (Alcohol X Expectancies) on attentional bias towards suicide-related cues (Stroop interference score, calculated by subtracting the response latencies for neutral words from the latencies for suicide-related words) will be estimated using a general linear model of the form $\hat{Y} = \beta_0 + \beta_1 Alcohol + \beta_2 Expectancies + \beta_3 Alcohol \times Expectancies$, where \hat{Y} is the average Stroop

interference score, *Alcohol* is a binary indicator (1=yes, 0=no) of assignment to alcoholic beverage intake, and *Expectancies* is a continuous score of alcohol expectancies (higher scores indicate higher expectancies). The coefficient β_2 estimates the differential effect of expectancies conditional on alcohol intake. With the model, we

will estimate Stroop inference scores by alcohol conditions at the mean expectancy and ± 1 SD away from the mean, expecting that in the alcohol condition, expectancies will have a stronger association with attentional bias towards suicide scores. Measures of effect size (e.g. R², partial eta², Cohen's r) will be used to aid in interpretation. Inferences will be conducted using confidence intervals for the comparisons of interest.

Power and Sample Size Considerations

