Individually Randomized Group-Treatment Trial Consideration: Note that this is an experimental design that randomizes participants to groups (alcohol or placebo and negative mood or positive mood induction). Participants will experience these manipulations independently (i.e., participants will not be interacting with one another). Nonetheless, the same research personnel will likely carry out the mood induction and alcohol administration manipulations with several different participants. Thus, some may designate this research as an "Individually Randomized Group-Treatment Trial," given the potential for nested data within research personnel. Because the mood induction and alcohol administration procedures are significantly standardized, we do not expect the effectiveness of these manipulations to vary across research personnel. However, we will collect data on who administers these protocols and examine differences across personnel to validate this assumption. If significant variation is discovered, we will *employ fixed effects* to account for these issues.

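### The H4 model leaves out the randomised mood factor. This is not an error, but adding Mood and Alcohol x Mood, suitably coded, costs almost nothing and fixes what the H4 alcohol effect and predicted means refer to.

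*SAP*

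**What the plan says.** The protocol (Approach) describes a "2x2, between subjects design (alcohol-placebo X negative mood-positive mood, baseline levels of expectancies". The SAP (Individually Randomized Group-Treatment Trial Consideration) confirms that the trial "randomizes participants to groups (alcohol or placebo and negative mood or positive mood induction". Mood is therefore assigned by randomisation, while expectancies are measured at baseline.

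H3 in the SAP includes Mood and Alcohol x Mood, and predicts an ordering of the four cells in which both negative-mood cells score above both positive-mood cells. There, Mood "is a binary indicator of assignment to the positive vs. negative mood induction (1 vs. 0".

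H4 has no mood term in either document. The protocol (Analytic plan, H4) says "The interactive effect of alcohol expectancies and AUA on suicide-related attentional bias will be estimated using a general linear model of the form" and then lists Alcohol, Expectancies and their product. The SAP (Specific Aim 4, Hypothesis 4, Analysis) gives the same three terms for "The interactive effect of expectancies and alcohol (Alcohol X Expectancies) on attentional bias towards suicide-related cues". From that model it "will estimate Stroop inference scores by alcohol conditions at the mean expectancy and ± 1 SD away from the mean". Neither document mentions centring Expectancies.

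The SAP (Statistical Design) also says that participants "not responding adequately to the mood induction will be removed from the initial analyses". The protocol (Manipulation of AUA and Mood) says the combined induction "has been shown to be effective in inducing a temporary negative mood state in 75% of subjects". It gives no matching figure for the positive induction.

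**The concern.** A randomised factor that is expected to affect the outcome would normally be in every model of that outcome. Leaving it out of H4 has two consequences.

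- **Precision.** Any mood effect becomes residual variance in H4.
- **Meaning.** Without Mood, the H4 alcohol effect and the predicted means average over whichever mood mix is analysed. Randomisation makes that mix close to even, but failures are removed afterwards. The only success rate the protocol gives by mood is for the negative state, so an even mix after removal is not assured.

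H4 will report effect sizes and predicted means with 68% intervals rather than tests, so readers need to know which population mix those estimates describe.

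**Working it through.** **Inputs.** From the SAP (Power and Sample Size Considerations): 30 per cell (N = 120), outcome SD 1, 68% intervals. From the protocol (Preliminary Data): mood effect d = .32, n = 23, not significant. Its standard error is about √(4/23) = .42. Assumed: d = 0 and d = .5 as a range, normally distributed expectancies with SD 1, residual SD 1.

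**The plan's own figures.** These are for H3; none is given for H4. With z(.84) = .9945:
- alcohol effect within a mood: .9945 x √(2/30) = .257, stated as .26
- Alcohol x Mood: .9945 x 2/√30 = .363, stated as .36

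Both reproduce.

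**Precision in H4.** In a balanced design a mood effect d adds d²/4 to the residual variance, so the half-width without Mood is larger by about √(1 + d²/4). This is √1.0256 = 1.013 at d = .32 and √1.0625 = 1.031 at d = .5. Against this, two extra terms cost about 0.9% on Alcohol x Expectancies through chance correlation with expectancies. Simulated 68% half-widths (12,000 runs, no Alcohol x Mood interaction):

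| Mood effect d | Alcohol x Expectancies: without → with mood terms | Alcohol effect at mean expectancy: without → with |
|---|---|---|
| 0 | .1863 → .1880 (+0.9%) | .1827 → .1828 (0%) |
| .32 | .1886 → .1879 (-0.4%) | .1851 → .1828 (-1.3%) |
| .5 | .1924 → .1882 (-2.2%) | .1886 → .1829 (-3.0%) |

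Break-even for Alcohol x Expectancies is where √(1 + d²/4) = 1.009, that is d of about .27.

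**Coding.**
- With Mood as a main effect only, 0/1 coding leaves the Alcohol half-width at .183.
- With 0/1 Mood and Alcohol x Mood, the Alcohol coefficient becomes the effect in the negative-mood group, and its half-width rises to .259 (√2 x .183).
- With -.5/+.5 coding and the product, the coefficient is the equal-weight average over moods, with half-width .183.
- Expectancies needs centring too. In the protocol's college sample the suicide-related expectancy score had mean 53.83 and SD 23.70, so a score of 0 lies 53.83/23.70 = 2.27 SD below the mean. Uncentred, the Alcohol coefficient is the effect at that point, with SE .1826 x √(1 + 2.27²) = .45 instead of .18. Predicted means are not affected by this.

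**Mood mix.** Assume 25% of negative-mood and no positive-mood participants are removed in both beverage arms, from 150/4 = 37.5 per cell. The negative share is 28.125/(28.125 + 37.5) = .429 in each arm.
- Predicted means at d = .32, no interaction: (.429 - .5) x .32 = -.023 SD.
- Alcohol effect, no Alcohol x Mood interaction: no shift, because both arms have the same mix.
- Alcohol effect, with interaction D (effect in negative minus effect in positive mood): (.429 - .5) x D. This is -.026 SD at an assumed D = .36 and -.071 SD at D = 1. With whole-number cells of 28 and 38 the share is .424, and the shift at D = 1 is -.076.

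In simulation with 28 and 38 per cell, the five-term centred model brought these shifts to within .004 of zero. Adding Mood alone left the shift in the alcohol effect unchanged, so Alcohol x Mood is needed as well.

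**The case against.** The strongest reply is that H4 is about Alcohol x Expectancies, which the omission does not bias. At the only documented mood effect the interval narrows by 0.4%, and with d = .32 known only to a standard error of about .42, the documents cannot show that it narrows at all. This stands, and it is why the point is minor.

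The SAP also plans for 30 in every cell and expects at least 75% induction success without splitting it by mood. The uneven mix is therefore an assumption. So is any removal that differs by beverage. For example, 50% v 25% of negative-mood participants gives shares of .333 and .429 and a shift of (.333 - .429) x .32 = -.03 SD, but no passage suggests such a difference. Equal weighting of moods is also a choice, since the documents do not say how H4 means should be weighted. These limits hold. The answer is that the choice should be made in advance and not left to the exclusions.

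A reader might infer three stronger claims that the documents do not support:
- **That the H4 interaction is biased.** Mood is randomised. Even after exclusions, the mix would have to be related to expectancies to shift the product term, and nothing in the documents suggests that.
- **That the plan contradicts its aim of studying alcohol, mood and expectancies together.** The protocol lists mood and expectancies as separate conditional effects, and its Innovation section leaves their joint interaction to future work. No three-way term is owed.
- **That baseline mood scores or sex should also be adjusted for.** The documents give no correlation of either with the Stroop score.

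**Conclusion.** Minor. The planned H4 model is legitimate, and its main target is not biased by leaving Mood out. Adding the mood terms is a near-free improvement whose main value is clarity: the alcohol effect and predicted means would refer to a stated, equal mood mix. The expected precision gain is around 1% or less at the partial test's mood effect and about 2% to 3% at d = .5, with a 0.9% loss on the interaction if mood has no effect. Under the assumed uneven removal the shifts are about -.02 SD in predicted means. In the alcohol effect they run from zero to between -.07 and -.08 SD, the latter only with an Alcohol x Mood interaction as large as 1. All are under half of the .18 half-width.

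Precision figures use the SAP's 30 per cell, while the mix scenario starts from 37.5 randomised per cell. At about 28 per cell, half-widths grow by √(30/28) = 1.035 and the conclusion is the same. A mood term does not repair other selection caused by removing participants after randomisation.

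**What to change.** In the SAP (Hypothesis 4, Analysis) and the protocol (Analytic plan, H4), state the model as Alcohol, Mood, Alcohol x Mood, Expectancies and Alcohol x Expectancies. Code Mood -.5/+.5 and centre Expectancies at the sample mean. The Alcohol coefficient is then the effect at mean expectancy, averaged equally over moods. Do not carry over the 0/1 Mood coding from H3 together with its product, because that changes what the Alcohol coefficient means. Report predicted means at the mean and ±1 SD expectancy averaged equally over the two mood conditions, and say so.

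Cost: wording only, using data already planned. Residual degrees of freedom go from 116 to 114 at N = 120. The Alcohol x Expectancies interval is at most about 0.9% wider, and that only if mood has no effect on the Stroop score.

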For this training grant, as a compromise between feasibility and precision of estimates, I propose to recruit 10 pre-pilot subjects and 150 subjects (approximately 38 per condition combination) over a 2.5-year period. Assuming that 25% of subjects may be excluded due to mood induction failure, we will have 30 subjects per condition. Rather than traditional significance testing, the goal of the project is to examine feasibility and tolerability of procedures and explore observed effect sizes. Inference will be conducted primarily by estimation of 68% confidence intervals to be used as reasonable ranges for observed effect sizes. Following the proposed analysis of Hypothesis 3, it can be shown using variance algebra that the standard error of the effect of alcohol intake on Stroop interference scores within each of the mood induction groups (positive or negative) is $SE_{Alco.Eff} = \sigma \sqrt{2/n}$, where σ is the standard deviation of the Stroop interference scores and *n* is the sample size per condition combination. Thus, the standard error of the differential effect of alcohol intake conditional on mood induction (i.e. the interaction term) is $SE_{Diff.Alco.Eff} = 2\sigma/\sqrt{n}$. With n = 30 and standardizing the Stroop interference scores (i.e. $\sigma = 1$) to express the confidence interval in terms of an effect size (Cohen's d), the half width of a 68% confidence interval for the standardized effect of alcohol intake within each of the mood induction groups is .26 and the half width of a 68% confidence interval for the standardized differential effect of alcohol intake conditional on mood induction is .36, which provide reasonable and tolerable uncertainty ranges.

For completeness, in terms of null hypothesis significance testing (not a primary goal of this study), at a significance level of .05 the sample size provides 80% power to detect a standardized effect of alcohol intake

within each of the mood induction groups of .72, and standardized differential effect of alcohol intake conditional on mood induction of 1.

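### The SAP's Hypothesis 4 text names β2 as the differential effect of expectancies; under its own model and 0/1 coding that effect is β3, and β2 is the placebo-condition slope

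*SAP*

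**What the plan says.** In the SAP, under Specific Aim 4, Hypothesis 4, the hypothesis is that the relation between suicide-related alcohol expectancies and attentional bias "will be stronger among those in the AUA condition compared to those in the placebo condition". The analysis paragraph names its target as "The interactive effect of expectancies and alcohol (Alcohol X Expectancies) on attentional bias towards suicide-related cues". The model has an intercept β0, β1 on Alcohol, β2 on Expectancies and β3 on the product. Alcohol "is a binary indicator (1=yes, 0=no) of assignment to alcoholic beverage intake", and Expectancies is continuous. The interpretation then reads: "The coefficient β_2 estimates the differential effect of expectancies conditional on alcohol intake". The paragraph goes on to plan predicted scores by alcohol condition at the mean expectancy and one SD either side, and confidence intervals for the comparisons of interest.

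Three other places bear on the point:

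- SAP, Specific Aim 3, Hypothesis 3, which has a model of the same structure, says that "the coefficient β_3 estimates the differential effect of alcohol intake conditional on mood induction".
- SAP, Power and Sample Size Considerations, uses differential effect to mean the product term. Quoted up to its closing bracket: "the standard error of the differential effect of alcohol intake conditional on mood induction (i.e. the interaction term".
- Protocol, Analytic plan, H4, gives the same equation and interprets none of its coefficients. It adds that linear contrasts and 68% intervals will be used for H3 and H4, without writing the contrasts out.

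**The concern.** The interpretation sentence attaches the hypothesised effect to the main-effect coefficient of Expectancies, although the equation just above it places the interaction on β3. It also disagrees with the way the SAP reads the parallel Hypothesis 3 model.

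This sentence is the only one in either document that says in words which Hypothesis 4 coefficient carries the hypothesised effect. An analyst who follows it would take the estimate and interval from the β2 row of the output. The result would then describe how expectancies relate to attentional bias in people given placebo. On its own it cannot show whether alcohol strengthens that relation.

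**Working it through.** **Inputs.** The model, the 0/1 coding of Alcohol and the hypothesis come from the SAP, Specific Aim 4. The Hypothesis 3 precision figures (n = 30 per condition combination, σ = 1, 68% intervals) come from the SAP, Power and Sample Size Considerations. The SAP gives no precision figure for Hypothesis 4.

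**1. Which coefficient is the differential effect.** The slope of the outcome on Expectancies is β2 + β3 × Alcohol.

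- Placebo (Alcohol = 0): β2
- Alcohol (Alcohol = 1): β2 + β3
- Difference: (β2 + β3) − β2 = β3

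**2. What β2 would report in two simple cases.**

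| Placebo slope | Alcohol slope | True difference | β2 | β3 |
|---|---|---|---|---|
| 0.3 | 0.3 | 0 | 0.3 | 0 |
| 0 | 0.5 | 0.5 | 0 | 0.5 |

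In the first case β2 suggests an effect where there is none. In the second it misses the effect completely.

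**3. Whether another coding rescues the sentence.** Least squares on one simulated data set (120 subjects, 60 per beverage arm, illustrative slopes and residual SD) gave a placebo slope of −0.0022, an alcohol slope of 0.6559 and a difference of 0.6580 (computed before rounding).

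| Coding | β2 | What β2 is |
|---|---|---|
| Alcohol 0/1, as in the SAP | −0.0022 | placebo slope |
| Alcohol 0/1, expectancies mean-centred | −0.0022 | placebo slope |
| Alcohol ±0.5 | 0.3269 | average of the two slopes |
| Alcohol reversed | 0.6559 | alcohol slope |

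β2 is never the difference. In every row β3 has magnitude 0.6580, and its sign flips under reversed coding.

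**4. Effect on the interval.** Because Alcohol is fully interacted with Expectancies, the β2 estimate equals the slope fitted to the placebo arm alone. The alcohol arm affects its interval only through the pooled residual variance s². Write SS_plac and SS_alc for the expectancy sums of squares within each arm.

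- Var(β2) = s² / SS_plac
- Var(β3) = s² (1/SS_plac + 1/SS_alc)

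Both use the same s² and the same degrees of freedom, so

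half-width(β2) / half-width(β3) = √[SS_alc / (SS_alc + SS_plac)].

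The ratio is below 1 whatever the outcome scale, residual SD or confidence level. The documents do not give SS_alc/SS_plac, so a range is assumed:

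| SS_alc / SS_plac (assumed) | Ratio of half-widths | β2 interval narrower by |
|---|---|---|
| 0.5 | √(0.5/1.5) = .577 | 42% |
| 1 | √(1/2) = .707 | 29% |
| 2 | √(2/3) = .816 | 18% |

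**5. The SAP's own figures for the analogous gap in Hypothesis 3.** The SAP states that "the half width of a 68% confidence interval for the standardized effect of alcohol intake within each of the mood induction groups is .26", and that the half width of the 68% "interval for the standardized differential effect of alcohol intake conditional on mood induction is .36". Both reproduce with z(.84) = .9945:

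- simple effect: .9945 × √(2/30) = .257, stated as .26
- differential effect: .9945 × 2/√30 = .363, stated as .36
- ratio: .257/.363 = 1/√2 = .707

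These are alcohol effects within mood groups, not expectancy slopes. They show only that the SAP itself treats a simple effect and a differential effect as different quantities with different precision.

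**The case against.** The strongest reply is that this is a slip of one character which the surrounding text already resolves. The target is named as the interaction, the equation puts the product on β3, the hypothesis is stated as a difference between conditions, and predicted scores are planned by condition. The Protocol also plans linear contrasts for H4. A careful analyst would probably reach β3, and the aim is exploratory in a pilot whose main purpose is feasibility. All of this stands, and it is why the point is minor. It does not make the sentence true. The Protocol's contrasts are not written out, so they do not correct it, and predicted scores alone do not supply an interval for the slope difference.

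Three narrower points also have force:

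- It would be too strong to say that β2 tells us nothing about the interaction. It is one of the two slopes being compared, and the estimates of β2 and β3 have correlation −√[SS_alc/(SS_alc + SS_plac)], about −.71 with equal sums of squares. The accurate statement is that β2 alone cannot identify the difference.
- The main harm would be reporting the wrong quantity. The narrower interval is secondary, and its size rests on an assumed range.
- This is an error of notation and internal consistency. The choice of model is not in dispute.

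A subscript could in principle be misread when text is extracted from a PDF. The subscripts in the equation of the same paragraph came through cleanly, and nothing suggests a misreading here.

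**Conclusion.** The point holds, as a minor error. The interpretation sentence for Hypothesis 4 is wrong under the SAP's stated model and coding: the differential effect is β3, β2 is the placebo-condition slope, and β2+β3 is the alcohol-condition slope. This is algebra and rests on no assumption about the data.

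If the sentence were followed literally, the reported estimate would answer a different question. Only the percentages for the narrower interval depend on an assumption, namely the ratio of expectancy sums of squares between arms. Nothing else in the plan is affected: the equation is sound, the planned predicted scores would be correct, and the stated sample-size, power and precision figures concern Hypothesis 3.

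**What to change.** In the SAP, Specific Aim 4, Hypothesis 4, Analysis, replace β2 with β3 in the interpretation sentence, and add:

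> β2 is the expectancy slope in the placebo condition and β2+β3 is the slope in the alcohol condition.

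The Hypothesis 4 result is then read from β3 and its confidence interval, in line with the treatment of Hypothesis 3. The cost is one subscript and one sentence of SAP wording. Data, model, predicted scores, sample size and precision figures do not change.
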